## 9.6 SAMPLE SIZE CALCULATION

Total POSAS scores range from 12 to 120. Though the POSAS has not been used to assess scarring after trigger finger release, the tool is validated with high internal consistency and reliability.

The trial will be powered to detect a difference in POSAS score of 10, deemed to be clinically significant by the investigators. The POSAS standard deviations in studies previously published on carpal tunnel release and carotid endarterectomies ranges from 1.0 to 11.0. To detect a mean difference in POSAS score of 10 points (SD = 8) with a two-sided significance level of 5% and power of 80% with equal allocation to two arms would require 12 patients in each arm of the trial. Additional subjects may be enrolled, as needed to achieve 12 patients in each treatment arm, in the event of patient death or withdrawal from the study.

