### 6.2 STANDARD AND RESEARCH PROCEDURES

All evaluations, procedures performed, and information obtained during pre-operative and post-operative visits will be within the standard of care with the exception of the POSAS questionnaire. The POSAS questionnaire contains a Patient Scale to be completed by the patient and an Observer Scale to be completed by the patient's surgeon-of-record. The Patient Scale is comprised of 6 questions regarding pain, itching, color, stiffness, thickness, and irregularity of their scar scored

numerically from 1 to 10. There is a 7th question, also on a scale of 1 to 10, that asks the patient for their overall opinion of the scar.

The POSAS questionnaire will be completed by patients at 1 week, 1 month, and 6 months post-operatively. In an effort to minimize inconvenience and avoid undue stress to the subjects, they will be given unlimited time to complete the questionnaire and will be allowed to skip questions as desired.

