## 8 OUTCOME MEASURES AND SUMMARY OF METHODS OF DATA COLLECTION

### 8.1 OUTCOME MEASURES

#### 8.1.1 PRIMARY OUTCOME MEASURE

Primary outcome measures include scarring based on Patient and Observer Scar Assessment Scale (POSAS) scores administered 1 week, 1 month, and 6 months post-operatively between patients treated with endoscopic versus open surgical release of the A1 pulley.

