### 9.3 HYPOTHESIS AND METHODS OF ANALYSIS

We hypothesize that patients treated with the retrograde endoscopic approach will have improved scarring compared to patients treated with the open approach, based on POSAS scores obtained at 1 week, 1 month, and 6 months post-operatively. We also hypothesize that the patients in the endoscopic treatment arm will have a faster recovery (return to work sooner with fewer days of occupational therapy), have higher overall satisfaction (scale 1 to 10) and use less pain medication. We anticipate that the two treatments will not differ significantly in complication or recurrence rate.

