#### 9.3.1 PRIMARY OUTCOME MEASURE ANALYSIS

Primary outcome measures of POSAS scores at 1 week, 1 month, and 6months post-operatively will be analyzed using descriptive statistics, including n, mean, standard deviation, median, minimum, maximum, and skewness.

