## 9.5 EXPLORATORY ANALYSES

POSAS scores at 1 week, 1 month, and 6 months post-operatively will be analyzed between patients treated with endoscopic versus open release using 2-sample t-tests. Differences in pain medication use, days before return to work, duration of OT, operative time, overall satisfaction, complication and recurrence rates between patients treated with endoscopic versus open surgical release of the A1 pulley will be tested for significance using 2-sample t-tests. Additional analyses of possible relationships between outcomes may also be performed using appropriate inferential tests.

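### Section 9.6 powers the trial for a 10-point POSAS difference, but no visit and no primary test is named to carry that power

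*Combined protocol and SAP*

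**What the plan says.** **Sizing.** Section 9.6 opens its calculation with "The trial will be powered to detect a difference in POSAS score of 10, deemed to be clinically significant by the investigators". With an SD of 8 it concludes that a two-sided "significance level of 5% and power of 80% with equal allocation to two arms would require 12 patients in each arm". It names neither a visit nor a test.

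**Hypothesis.** Section 9.3 expects the endoscopic arm to show "improved scarring compared to patients treated with the open approach, based on POSAS scores obtained at 1 week, 1 month, and 6 months post-operatively".

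**Primary outcome.** Section 8.1.1, repeated in 9.2.1, makes the primary outcome POSAS "scores administered 1 week, 1 month, and 6 months post-operatively", with no visit put first.

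**Primary analysis.** Section 9.3.1 says these scores "will be analyzed using descriptive statistics, including n, mean, standard deviation, median, minimum, maximum, and skewness". It plans no between-arm difference, interval or test.

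**Between-arm tests.** These are in Section 9.5, under exploratory analyses: POSAS at all three visits "will be analyzed between patients treated with endoscopic versus open release using 2-sample t-tests". No multiplicity rule is given.

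**Status of the work.** The introduction to Section 9 describes all analyses as descriptive. The synopsis (Section 1.1, Statistical Methods) justifies 24 patients as enough for descriptive summaries and exploratory work, and gives no power statement.

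**Score.** The sample-size text says "Total POSAS scores range from 12 to 120". Section 6.2 explains that the questionnaire "contains a Patient Scale to be completed by the patient and an Observer Scale to be completed by" the surgeon of record. The outcome and analysis sections refer only to POSAS scores, without saying whether the total or one of the two scales is meant.

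**The concern.** A statement of 80% power at two-sided 5% is a statement about one specified test. Here the test that would carry it is exploratory, is run three times, and is absent from the primary analysis. The main comparison therefore has two statuses, and each causes a problem.

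- **Read as confirmatory.** Nothing says which of the three visits decides. The emphasis can be placed after the results are known, and the 5% of Section 9.6 is not controlled. Scars may compare differently at 1 week and at 6 months, so the choice could change the conclusion.
- **Read as descriptive or exploratory.** The power statement supports nothing that is planned, and the hypothesis in Section 9.3 should not be reported as tested. A reader who sees three t-tests beside an 80% power claim may still take any p-value below 0.05 as the powered result.

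The unspecified score adds to this. Ten points on the total is not the same effect as ten points on the patient or the observer scale.

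**Working it through.** **Inputs from Section 9.6:** difference 10, SD 8, two-sided 5%, 80% power, equal allocation, 12 per arm. The standardised difference is 10/8 = 1.25.

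**Inputs assumed, because the documents give none:** a between-visit correlation of 0 to 0.9, and a success rule across visits (both natural rules are shown in steps 3 and 4).

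**1. The plan's own figure.** Power of the two-sample t-test from the noncentral t distribution, with 2n − 2 degrees of freedom and noncentrality 1.25 × √(n/2):

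| n per arm | Power at 5% |
|---|---|
| 11 | 79.6% |
| 12 | 83.3% |

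Twelve is the smallest n that reaches 80%, so Section 9.6 reproduces. It does so for one comparison at one time point.

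**2. Setting the sections side by side.** A single comparison at 5% is sized in 9.6. Three unranked visits are primary in 8.1.1 and 9.2.1. The primary analysis in 9.3.1 contains no comparison. Three t-tests are planned in 9.5, as exploratory. No section links the single sized comparison to one of the three tests.

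**3. If confirmatory, and any one significant visit counts.** With no true difference and three unadjusted 5% tests, the chance of at least one false positive at correlation 0 is 1 − 0.95³ = 14.3%. With correlation, by simulation (1,000,000 trials per setting, 12 per arm):

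| Correlation | 0 | 0.3 | 0.5 | 0.7 | 0.9 |
|---|---|---|---|---|---|
| Unadjusted | 14.2% | 13.7% | 12.7% | 11.1% | 8.5% |
| Bonferroni (0.05/3 = 0.0167 each) | 4.9% | 4.8% | 4.5% | 4.0% | 3.0% |

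**4. If confirmatory, and all three visits must be significant.** The false-positive chance is then well under 5% (about 0.01% to 2.2% for correlations 0 to 0.9). With a true difference of 10 and SD 8 at every visit, power at 12 per arm is about 58% at correlation 0, 66% at 0.5 and 76% at 0.9. All are below the stated 80%.

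**5. If three primary visits are kept with Bonferroni.** Power at one given visit, at alpha 0.0167:

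| n per arm | 12 | 14 | 15 |
|---|---|---|---|
| Power | 68.0% | 76.7% | 80.3% |

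At least 80% at each visit therefore needs 15 per arm, which is 2 × 3 = 6 more patients.

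**6. Precision at the planned size.** The 95% CI half-width for the mean difference is t(0.975, 22 df) × 8 × √(2/12) = 2.074 × 3.266 = 6.8 points.

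**The case against.** The strongest reply is that the plan is exploratory and says so. The synopsis, the introduction to Section 9, Section 9.3.1 and the heading of Section 9.5 all point that way, and no section calls any test confirmatory. Choosing the size of an exploratory study with a conventional power formula is not in itself a contradiction, and on this reading no multiplicity rule is owed. This largely stands. It makes the error rates in step 3 conditional, but it does not rescue the power statement, which then belongs to no planned conclusion and should go.

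Second, the 8.5% to 14.3% depends on a success rule that the plan does not state, and the wording of Section 9.3 fits an all-visits reading at least as well. That is fair. Under that reading the false-positive rate is not inflated, but power falls short of the stated 80% (step 4).

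Third, the 68.0% is power at one given visit, whereas the false-positive rates count any visit. Under the any-visit rule, with a 10-point difference at all three visits, Bonferroni power at 12 per arm is about 97%, 89% and 78% at correlations 0, 0.5 and 0.9. The 15 per arm is therefore needed only if each visit must have its own 80%.

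Two smaller points also stand. The t-tests at all three visits are prespecified, so the risk is selective emphasis and not an unplanned test. The total score can be inferred from its mention just before the calculation, although the outcome sections should state it.

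**Conclusion.** The concern holds and should be fixed. The arithmetic of Section 9.6 is sound; the fault is that its 5% and 80% attach to no named visit and no primary test, while the rest of the plan treats the comparison as descriptive or exploratory. This is an inconsistency in the current text, not merely a missing detail.

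Its numerical size depends on the reading. The 8.5% to 14.3% is not the trial's error rate: it requires confirmatory status, an any-visit rule and the assumed correlations. The 58% to 76% requires an all-visits rule and a 10-point difference with SD 8 at every visit. On the exploratory reading there is no error rate to inflate, only a power claim and a hypothesis that the planned analysis does not test. The conclusion itself needs none of these assumptions.

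**What to change.** Before outcome data are seen, take one of two routes, at the investigators' choice.

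**(a) One primary comparison.** In Sections 8.1.1 and 9.2.1, name one visit and the total POSAS score (12 to 120) as the primary endpoint. In 9.3.1, make its analysis the between-arm mean difference with 95% CI and a two-sided 5% two-sample t-test. Move the other two visits to secondary, and align the introduction to Section 9, Section 9.5 and the synopsis. Twelve per arm stays, with 83.3% power under a difference of 10 and SD 8. Section 9.6 cites SDs up to 11.0, at which power would be 56.7%; this should be stated beside the 83.3%. Because Section 6.2 lets patients skip questions and Section 9 excludes imputation, also say how a total with missing items is handled.

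**(b) A descriptive trial.** Delete the power claim from 9.6, present the hypothesis in 9.3 as exploratory, and, if wished, justify 12 per arm by precision (95% CI half-width about 6.8 points at SD 8).

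If all three visits are to stay primary, specify Holm or Bonferroni and restate the power: 68.0% at one given visit with Bonferroni at 12 per arm, or 15 per arm (6 more patients) for at least 80% at each visit.

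**Cost.** Routes (a) and (b) change text only and add no patients, but as amendments they need IRB approval under the Statement of Compliance. Under (a), a benefit seen only at another visit becomes secondary evidence. Under (b), no confirmatory claim can be made.

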## 9.7 INTERIM ANALYSES

Not applicable.

## 9.8 PROTOCOL DEVIATIONS

Protocol deviations may include:

- Deviations from the protocol, contrary to protocol specifications (i.e., deviations from the protocol, eligibility, visit windows, etc.).
- Deviations affecting the endpoint outcome not previously specified in the protocol (i.e., deviation that had not been previously considered in the protocol or eligibility criteria, however having a clear impact on the primary outcome measure)

All protocol deviations will be reviewed and categorized as major (i.e., those that affect measurement or interpretation of the primary endpoint) or minor (those not affecting the primary endpoint).

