#### 6.1.3 FOLLOW-UP VISITS

Subjects will be required to attend post-operative visits at 1 week, 1 month, and 6 months post-operatively, as is the standard of care. Review of medical history and physical examination will be conducted at all post-operative visits. At 1 week, 1 month, and 6 months post-operatively, pain medication use, days before return to work, duration of occupational therapy, as well as POSAS scores will be obtained and photos will be taken.

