### 9.1 POPULATIONS FOR ANALYSES

All subjects will be included in the full analysis population. The per protocol population is defined as subjects who have not had any major protocol deviations throughout the study (Section 9.8) and will be analyzed as the primary study group. Other subgroups may be analyzed as detailed in the subgroup analyses section. Subjects that have been discontinued will be excluded from data analysis.

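### Membership of the primary (per protocol) population turns on a deviation's effect on the primary endpoint, with no requirement to classify deviations before scores are seen or masked to arm and POSAS

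*Combined protocol and SAP*

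**What the plan says.** Two sections of the combined protocol and SAP work together.

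- **Section 9.1 (Populations for Analyses).** "The per protocol population is defined as subjects who have not had any major protocol deviations throughout the study", with a cross-reference to Section 9.8. This population "will be analyzed as the primary study group". A full analysis population is also named, but it is not the primary one. The section ends: "Subjects that have been discontinued will be excluded from data analysis".
- **Section 9.8 (Protocol Deviations), what counts as a deviation.** One bullet covers departures from what the protocol specifies. The other covers departures nobody foresaw, described as a "deviation that had not been previously considered in the protocol or eligibility criteria, however having a clear impact on the primary outcome measure".
- **Section 9.8, grading.** "All protocol deviations will be reviewed and categorized as major (i.e., those that affect measurement or interpretation of the primary endpoint"; deviations without such an effect are minor.

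Neither section lists major deviations, names who grades them, places the grading before the scores are seen, or requires masking to arm or POSAS. No masking is described elsewhere. Section 6.2 has the operating surgeon complete the Observer Scale.

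**The concern.** A per protocol set can be trusted when its exclusions could have been made without knowing the results. Here the label that removes a subject from the primary group is defined by effect on the primary endpoint. An unforeseen event qualifies as a deviation through its clear impact on that same outcome. A deviation admitted on that ground can hardly then be graded minor, because minor means that the primary endpoint is unaffected.

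A reviewer with the scores in hand could therefore stay within the wording and treat an irregularity as major in a subject with a poor scar score, yet minor in a subject with a good one. If this happened differently in the two arms, the endoscopic-versus-open difference would be biased. With 12 subjects per arm, each exclusion carries weight. The problem reaches subjects who were operated on and fully followed, so it is separate from the handling of discontinued subjects.

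**Working it through.** **Inputs from the plan.** Section 9.6 gives a target difference of 10 POSAS points, SD 8, two-sided 5%, 80% power, 12 per arm, and a published SD range of 1.0 to 11.0. Section 9.5 gives two-sample t-tests. The documents give no expected number of deviations, so the exclusion patterns below are assumptions.

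**Step 1: the plan's own figure.** The normal approximation is n = 2(1.960 + 0.842)² × 8² / 10² = 2 × 7.85 × 0.64 = 10.05, rounded up to 11 per arm. The exact t-test calculation needs 11.09, so 12 per arm, with power 83.3%. The stated 12 is reproduced; the sample size is not in question.

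**Step 2: benchmark.** The simulation used 200,000 trials with normal scores, SD 8, no true difference, 12 per arm, a pooled t-test and one time point. Worst means the highest score.
- With nobody removed, rejection favouring endoscopic is 2.5% (about 5% two-sided).
- With two endoscopic subjects removed at random, the bias is 0.0 points and the two-sided error 5.1%.

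Losing subjects does not in itself bias the comparison. Only selection on outcome does.

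**Step 3: upper bound.** The extreme score is removed in every trial.

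| Removed | Shift favouring endoscopic (points) | False positives favouring endoscopic |
|---|---|---|
| Worst endoscopic | 1.2 | 6% |
| Two worst endoscopic | 2.2 | 11% |
| Worst endoscopic and best open | 2.4 | 13% |

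The shifts can be checked by hand. Removing the largest of 12 scores lowers the arm mean by SD × E(largest)/11. The expected largest and second-largest of 12 standard normal values are 1.629 and 1.116. So one removal gives 8 × 1.629/11 = 1.18, two give 8 × (1.629 + 1.116)/10 = 2.20, and one from each arm gives 2 × 1.18 = 2.37.

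The shift scales with the SD. Over 1.0 to 11.0, one endoscopic removal shifts the difference by 0.15 to 1.6 points and two by 0.27 to 3.0.

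**Step 4: a less extreme pattern.** Deviations arise independently of score in 5% to 20% of subjects, and a partial reviewer drops only the unfavourable ones.
- Dropping only endoscopic deviators scoring worse than their arm's median: shift 0.2 to 0.7 points, false positives favouring endoscopic 2.9% to 4.0%.
- Also dropping open deviators scoring better than their arm's median: shift 0.3 to 1.5 points, false positives 3.1% to 5.9%.

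**Step 5: against the target.** The largest shift in Step 3 is 2.4/10 = 24% of the target difference, and the largest in Step 4 is 1.5/10 = 15%. Under no true difference, the two-subject worst case gives an observed benefit of 10 points or more in only about 1% of trials.

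**The case against.** The best defence is that Section 9.8 concerns the kind of departure, not the score. A breached smoking or wound-healing exclusion, or a POSAS taken at the wrong time, can be judged to affect measurement or interpretation without looking at any result. The clear-impact wording sits in the bullet on what counts as a deviation, not in the definition of major. That reading is open and may be the intended one, but the text does not confine the rule to it.

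The setting also tempers the concern. Section 9.3.1 makes the primary analysis descriptive, and Section 9.5 labels the t-tests exploratory. Summaries may be produced for the full analysis population too, so a divergence could be noticed, and Section 12.3.1 has deviations recorded. All of this stands. It does not remove the problem, because selective exclusion biases a mean whether or not a test follows, and the group singled out as primary is the exposed one.

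Four stronger readings are tempting but not supported:

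- *The reviewer must look at the scar score.* The rule permits this but does not require it, and no subject leaves the population under this rule without some deviation.
- *The people grading deviations know the arm.* No reviewer is named. Absent masking and a surgeon-completed Observer Scale make this plausible, but it is an inference.
- *One or two reclassified subjects could produce the hoped-for benefit.* The shifts fall well short of 10 points.
- *Late visits will be graded case by case because no window exists.* Section 9.8 mentions windows and Section 6.1.3 gives only nominal times. However, the synopsis refers to the Section 1.2 schema for the schedule, and that schema is missing from the text available for this review. Windows may be stated there.

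**Conclusion.** The point holds as a weakness in the rule, not as evidence that selection will occur. The primary population depends on a label tied to effect on the primary endpoint, and nothing requires that label to be fixed independently of scores and arm.

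At SD 8, 12 per arm and no true difference, the upper bound for one or two removals is a spurious benefit of 1.2 to 2.4 points, with false positives favouring endoscopic of 6% to 13% against 2.5%. A less extreme pattern gives about 0.2 to 1.5 points and 3% to 6%. These sizes rest on assumed exclusion patterns, normal scores and a single time point.

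This should be fixed. Given the descriptive analysis and the modest likely size, it is not among the changes without which the study could not proceed.

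**What to change.** **Section 9.1.** Make all operated subjects with available POSAS data, analysed in their assigned arm, the primary study group, and keep per protocol as a supportive analysis. Reconcile this with the closing sentence that excludes discontinued subjects. As written, that sentence also sits awkwardly with a full analysis population meant to contain everyone.

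**Section 9.8.** Remove impact on the observed outcome as a ground for exclusion. Define major deviations by a list that can be applied without seeing POSAS, such as an eligibility breach, no A1 release performed, or a POSAS taken outside a stated window. Have the list applied and signed off, masked to arm and POSAS, before any between-arm summary is produced.

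**Cost.** Wording in two sections and one masked review of a deviation listing. The small downside is that a few imperfectly measured scores stay in the primary summary; the supportive per protocol analysis shows whether they matter.

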## 10 STUDY ADMINISTRATION PROCEDURES

### 10.1 SUBJECT ENTRY PROCEDURES

#### 10.1.1 OVERVIEW OF ENTRY PROCEDURES

Prospective subjects as defined by the criteria in Section 5.3 and 5.4 (inclusion/exclusion criteria) will be considered for entry into this study.

#### 10.1.2 INFORMED CONSENT AND SUBJECT PRIVACY

The purpose, procedures, risks, benefits, and alternatives to study participation will be discussed with each potential subject. Prior to any study-related procedures or change in treatment, subjects wishing to participate must give their written informed consent (IC). The subject must also give Authorization for Use and Release of Health and Research Study Information (HIPAA) and other written documentation in accordance with the relevant country and local privacy requirements (where applicable) prior to any study-related assessments/questionnaires. Subjects will be consented to provide a copy of all medical imaging (e.g. radiology) collected as standard-of-care or research during the study duration for inclusion in the study file. The Investigator will conduct the IC discussion and will document in the subject's medical records the process for acquiring IC and the subject's agreement or refusal to notify her primary care physician about the study. The subject should personally sign and date the IC form. The Investigator will retain the original copy of the signed IC form, and the subject will also receive a copy. Upon signing the IC form, the subject will receive a subject number that will be used on all documentation for the subject throughout the study. Subject numbers should be assigned in ascending order, and numbers should not be omitted or reused. The subject number is a unique identification for each subject.

